#### **10.16. Tapering Period**

All patients who discontinue early from study treatment during the open-label extension study will have their study medication tapered over a 3-week period, reducing their daily dose by one-third per week, and return immediately for a final visit. The patients will be instructed to take the tablets from their existing study medication bottles and to follow this tapering procedure:

- During the first week of tapering, patients will no longer take the afternoon dose.
- During the second week of tapering, patients will no longer take the morning and the afternoon doses.
- During the third week of tapering, patients will take no study medication (but will continue their existing background AEDs).

During the first year, these patients should then return for a final visit to complete all assessments and evaluations scheduled for Study Visit 5. During the second year, these patients should then return for a final visit to complete all assessments and evaluations scheduled for Study Visit 8. During the third year, these patients should then return for a final visit to complete all assessments and evaluations scheduled for Study Visit 11. During the fourth year, these patients should then return for a final visit to complete all assessments and evaluations scheduled for Study Visit 14 (Refer to Study Flow Chart in Appendix A).

During the tapering period, a new background AED should not be added until after the patient's final visit unless clinically necessary for patient safety. Unused current study medication bottles will be collected to ascertain compliance. Current study seizure

diaries will be collected and reviewed. Concomitant medications and AED usage will be documented, and adverse events will be recorded.

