## **11. STATISTICAL MEASUREMENTS, EVALUATIONS AND ANALYTICAL METHODS**

### **11.1. Assessment of Efficacy**

Monthly total seizure rates will be calculated for the entire open-label part of Study VRX-RET-E22-304 and described statistically. Monthly total seizure rates observed during the open-label extension period will be compared to the monthly total seizure rates observed during the Baseline phase of the double-blind study VRX-RET-E22-302. The percent change in monthly total seizure rates from the Baseline phase will be classified into <0, [0, 25), [25, 50), [50, 75), [75, 100] and described. The responder rate during the open-label study (defined as a reduction in seizure frequency  $\geq 50\%$ ) will also be summarized using descriptive statistics.

The number of seizure free days, in percent to the individual duration of the open-label treatment, will be calculated and summarized using descriptive statistics. This percentage will be classified into [0, 25), [25, 50), [50, 75), [75, 95), [95, 100), [=100] and described statistically.

All-cause withdrawal rates will be calculated as a percentage and respective "times to event" will be described by a Kaplan-Meier survival curve. Specific reasons for withdrawal will also be described separately.

This is an open-label extension study with the emphasis on safety. Efficacy is not the primary objective of this study unlike the double-blind study VRX-RET-E22-302. Descriptive statistics of efficacy measures such as number of patients, mean, standard deviation, median, minimum and maximum will be provided for continuous variables. The number and percentages in each category will be presented for categorical data. The pairwise t-test will be used to assess whether the retigabine treatment remains effective in the open-label extension study if necessary. The pairwise t-test may be sorted by the geographic region [Central/Eastern Europe vs. Rest of World (ROW)]. The safety assessments will use essentially the same descriptive statistics and pairwise t-test as mentioned above for efficacy. The complete details of efficacy analyses will be described in the Statistical Analysis Plan.

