#### 3.2.1 Efficacy Assessments

Patients will keep a seizure diary throughout the study. The anticonvulsant efficacy of retigabine will be evaluated by comparison of baseline seizure frequency (obtained during the 8-week baseline period of Study VRX-RET-E22-302) with seizure frequency obtained during retigabine therapy in this open-label extension study (VRX-RET-E22-304). The primary efficacy variable is the percentage change in the monthly seizure rate from the baseline phase to the open-label treatment phase. The proportion of responders (patients experiencing  $\geq 50\%$  reduction in seizure frequency) from baseline to the open-label treatment phase will be evaluated.

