#### 4.4 Efficacy Evaluation

“Monthly total partial seizure” as well as “monthly total seizure” rates will be calculated for the entire open-label part of Study VRX-RET-E22-304 and statistically described. “Monthly total partial seizure” rate is defined as the sum of total partial seizures throughout the open-label portion (of Study VRX-RET-E22-304), divided by open-label duration in days, standardized by 28 days (1 month). “Monthly total seizure” rate is defined as the sum of partial and generalized (or unclassified) seizures throughout the open-label duration in days, standardized by 28 days (1 month).

Monthly total partial seizure rates observed during the open-label extension period will be compared to the monthly total seizure rates observed during the Baseline phase of the double-blind study VRX-RET-E22-302. The baseline monthly total seizure rates will only be derived for patients who enter this open-label extension and have a monthly total partial seizure rate during the open-label extension period. The percent change in monthly total partial seizure rates from the Baseline phase will be classified into <0, [0, 25), [25, 50), [50, 75), [75, 100] with a description of the frequencies. The responder rate during the open-label study (defined as a reduction in seizure frequency  $\geq 50\%$ ) will also be summarized using descriptive statistics.

The monthly total partial seizure rates compared to the baseline monthly total partial seizure rate will be presented cumulatively for each timepoint (months 1, 3, 6, 9, 12, 16, 20, 24, 28, 32 and 36) during the open label extension period and separately for eleven cohorts of patients treated with retigabine for at least 1, 3, 6, 9, 12, 16, 20, 24, 28, 32 and 36 months. In each cohort, patients will be followed for entire indicated duration of treatment. For example, patients in the 36-month cohort will also be part of the shorter-duration cohorts.

A similar analysis will be repeated for the responder rate during the open-label study.

A plot of the median percent reduction from baseline in seizure frequency over time by duration of treatment will also be produced.

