## 4.5 Safety Evaluation

### 4.5.1 Extent of Exposure

Exposure Daily Dose is defined as the mean value of daily dosages of study drug, that is total dosage taken by a patient divided by number of days the patient participated in the study. The total dosage is defined as sum of the recorded doses in the Study Medication and Dose Change Log for each visit. The number of days patient participated in this study is defined as the period from the first dose date (Day 0) to the last recorded dose date. Descriptive statistics of the exposure daily dose of this study will be presented.

Extent of exposure is defined as the total number of days a patient is exposed to study drug. In calculation, the extent of exposure equals the total number of days from the first dose date (Day 0) to the last recorded dose date. If a patient is lost to follow-up, but the drug accountability log confirms that the patient has taken study drug, the last visit date of the treatment period will be used for calculation of extent of exposure. For better description, extent of exposure (in weeks) will also be categorized ( $\leq 1$ , (1-3], (3-6], (6-9], (9-12], (12-16], (16-20], (20-24], (24-28], (28-32], (32-36],  $>36$ ). Descriptive statistics for extent of exposure categorized by weeks will additionally be presented.

A by-patient listing of detailed exposure daily dose, dose modifications and extent of exposure to study drug will be provided. Any extreme values for both the exposure daily dose and the extent of exposure to study medications will be reported in the listings, in case that happens.

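### SAP 4.4 sets no end day for the open-label seizure rate and does not exclude the 21-day taper, so early leavers near the 50% cut can be misclassified in Tables 8, 10, 12 and 13

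*SAP*

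**What the plan says.** **Target.** SAP 3.2.1 and Protocol 10.2 compare the 8-week baseline of Study 302 with "seizure frequency obtained during retigabine therapy in this open-label extension study (VRX-RET-E22-304").

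**Computation.** SAP 4.4 says that the "rates will be calculated for the entire open-label part of Study VRX-RET-E22-304 and statistically described". The partial seizure rate is the "sum of total partial seizures throughout the open-label portion (of Study VRX-RET-E22-304), divided by open-label duration in days", scaled to 28 days. Protocol 11.1 uses the same whole-period wording: "Monthly total seizure rates will be calculated for the entire open-label part of Study VRX-RET-E22-304 and described statistically". A responder has a reduction of at least 50%. Percent seizure-free days is introduced relative to open-label treatment, but its formula divides by open-label duration in days. Neither document says on which day that duration ends.

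**Taper.** SAP 3.1 and Protocol 9 and 9.4 place a 3-week taper after treatment and before the 30-day post-study period. Protocol 10.16 drops one of the three daily doses in week 1 and a second in week 2. Then: "During the third week of tapering, patients will take no study medication (but will continue their existing background AEDs"). Diaries are collected and reviewed for this period, and the final visit follows it.

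**Exposure.** SAP 4.5.1 does define an end: "the extent of exposure equals the total number of days from the first dose date (Day 0) to the last recorded dose date". Protocol 11.2 and 12.4.1 equate the last dose with the end of the taper-off.

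**Reporting.** SAP 4.5.2 does not treat worsening of seizure frequency as an adverse event and leaves it to the efficacy analysis. No table or figure in the SAP summarises taper seizures separately.

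**The concern.** The stated target is response on drug, but the formula takes in whatever falls within an open-label period whose end is not fixed. Two programmers could follow SAP 4.4 faithfully and report different values for the primary efficacy variable.

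If the taper is included, the error is not uniform. The taper's share of the denominator is 21/(T + 21), where T is days on treatment: 41.2% at 30 days, 18.9% at 90, 10.4% at 180 and 1.9% at 1080. Someone who responded on drug but left early, for instance because of an adverse event, could be reported as a non-responder, while a long-stay patient would hardly move. The bias therefore depends on time to withdrawal.

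There is also a gap on the safety side. The primary objective is the safety of long-term therapy. Seizures on stopping the drug bear on that, but they would be pooled into an efficacy rate or left to listings.

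**Working it through.** The plan states no figure to reproduce; the study is descriptive and has no sample-size calculation. The check is a sensitivity calculation.

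**Inputs from the documents**
- Taper of 21 days: 14 dosed and 7 drug-free (Protocol 9.7.5, 10.16).
- Responder cut of 50% (SAP 4.4).
- In the predecessor extension, 18 of 222 patients stopped within 3 months and 41 of 222 within 6 months (Protocol 7.4).

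**Assumptions**
- T is days on treatment before the taper and r the on-drug reduction from baseline.
- m is the taper seizure rate divided by the baseline rate. The documents give no value for m, so three cases are shown.

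**Formula.** The reduction with the taper included is 1 − [T(1 − r) + 21m]/(T + 21). Setting this at 0.5 or more gives T(r − 0.5) ≥ 21(m − 0.5).

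- *Case A, rate returns at once to baseline (m = 1):* the reduction reads as rT/(T + 21), so the required r is 0.5(T + 21)/T. With only the 14 dosed days it is 0.5(T + 14)/T.
- *Case B, effect proportional to dose, with three equal daily doses:* taper weeks 1, 2 and 3 keep 2/3, 1/3 and 0 of the effect, which is worth 7(2/3 + 1/3 + 0) = 7 full-effect days. The required r is 0.5(T + 21)/(T + 7).
- *Case C, taper rate half of baseline (m = 0.5):* the right-hand side is zero, so the required r stays at 50%.

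| T (days) | A, 21 days | A, 14 days | B, 21 days | C |
|---|---|---|---|---|
| 30 | 0.5 × 51/30 = 85.0% | 0.5 × 44/30 = 73.3% | 0.5 × 51/37 = 68.9% | 50% |
| 90 | 0.5 × 111/90 = 61.7% | 0.5 × 104/90 = 57.8% | 0.5 × 111/97 = 57.2% | 50% |
| 180 | 0.5 × 201/180 = 55.8% | 0.5 × 194/180 = 53.9% | 0.5 × 201/187 = 53.7% | 50% |

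**One patient followed through.** With r = 60% in case A, the reported reduction is 0.6 × 30/51 = 35.3% at 30 days, 0.6 × 90/111 = 48.6% at 90 days (both non-responder) and 0.6 × 180/201 = 53.7% at 180 days (responder). Break-even is T = 21 × 0.5/0.1 = 105 days. If seizures rebounded to 1.5 or 2 times baseline, it would be 210 or 315 days.

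**Which outputs.** Tables 8, 10, 12 and 13 use the whole open-label period. Tables 9.1–9.11 and 11.1–11.11 are restricted to patients treated for at least the stated number of months and show only timepoints within that duration. Figure 1 is by duration of treatment. The taper can enter these only if taper days are themselves counted as treatment time.

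**How many.** 18/222 = 8.1% and 41/222 = 18.5% are all leavers, the second figure including the first, so they only bound the number affected. Only leavers who responded on drug and were close enough to the cut could lose responder status.

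**The case against.** **The text allows an on-treatment reading.** The target is frequency during therapy, treatment is described as followed by the taper, and seizure-free days are introduced relative to treatment. This stands to the extent that a reader should not infer that taper seizures are certainly counted, or that patients are certainly misclassified. No sentence says so. But none of those phrases is carried into the formula. The whole-period wording, the diary review during the taper and the statement that worsening belongs to the efficacy analysis all point the other way.

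**The seizures are not lost.** A reader might infer that taper seizures are reported nowhere. That is not so. Listings 7 and 8 give seizures by date and study day, and Listing 8 has status epilepticus columns. Events meeting the serious criteria are collected to 30 days after the last dose. What is missing is a separate summary. The sentence in SAP 4.5.2 about close monitoring does not supply it: it concerns patients who leave the double-blind period or decline the extension.

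**Case A is severe.** After the first step down, 900 or 1200 mg/day becomes 600 or 800 mg/day, still within the study's 600–1200 range. An immediate return to baseline is therefore close to the worst case unless seizures rebound above it. This stands, which is why cases B and C are shown.

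**Few patients may be affected.** Scaling the predecessor's rates to 510 patients gives about 41 and 94, and it is tempting to call these the patients affected. They are leavers, not misclassified patients. Lack of efficacy was the commonest reason for stopping, and a non-responder on drug cannot be turned into one by the taper. The 510 is also a ceiling. If entry followed the predecessor (222 of 397), about 510 × 222/397 = 285 would enter, with about 23 and 53 leaving by 3 and 6 months.

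**Efficacy is secondary and descriptive.** True. It limits the consequence but does not make the window any better defined.

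**Conclusion.** The point holds as a defect in the analysis window. SAP 4.4 does not fix when the open-label period ends for the rate, responder status or percent seizure-free days. Its literal reading admits 21 days of falling and zero dose, and the only end date the SAP defines for exposure still admits 14 reduced-dose days. Either conflicts with the stated on-therapy target.

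The size depends on the taper rate, which the documents do not give. At 30 treated days the bar for a responder ranges from 50% to 85%, with about 69% in between if effect tracks dose. At 90 days the two higher figures fall to 61.7% and about 57%, and at 180 days to 55.8% and about 54%. Reclassification needs three things together: the taper in the window, a taper rate above half of baseline, and either short treatment or a response near the cut. How many patients meet all three cannot be derived from the documents.

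On safety, the supportable statement is narrow: no table separates seizures on stopping retigabine, and worsening is kept out of adverse events.

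**What to change.** 1. In SAP 4.4, end both the seizure count and the denominator on the day before the taper starts, or at the last dose if treatment stops without a taper. Apply this to Tables 8, 10, 12 and 13.
2. Repeat those tables with the taper included, as a sensitivity analysis.
3. Add one descriptive table for patients who taper. It should give the 28-day seizure rate and any status epilepticus in the dosed taper weeks, in the drug-free week, in the last 28 days before the taper, and at the Study 302 baseline.

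The cost is SAP wording, a rerun of four tables and one small new table. The data are already planned: seizure dates in Listings 7 and 8, and a tapering-dose date in Listing 1. The Listing 1 heading does not say whether that date is the start or the end of the taper, so this should be confirmed, for example against the dose change log. Rates over one or two weeks will be imprecise and should be labelled so. No visits are added and the clinical taper is not changed.

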RM2009/00475/00  
 VRX-RET-E22-304

Program Path/sas program name

Run Date:

Valeant Pharmaceuticals North America  
Protocol Number: VRX-RET-E22-304

PAGE X OF X

FOOTNOTES:

A PATIENT CAN HAVE EPILEPSY HISTORY RECORDED FOR EACH TYPE OF EPILEPSY.

Valeant Pharmaceuticals North America  
 Protocol Number: VRX-RET-E22-304

PAGE X OF X

TABLE 5 CLINICAL GLOBAL IMPRESSION (CGI) - SEVERITY AT BASELINE  
 SAFETY POPULATION

STATISTICS	RETIGABINE (N=XXX)
CGI-SEVERITY	
N	xxx
MEAN	xxx.x
STD	xxx.xx
MEDIAN	xxx.x
MINIMUM	xxx
MAXIMUM	xxx
CGI-SEVERITY	
AMONG THE MOST EXTREMELY SEVERE	xxx (xx.x%)
VERY SEVERE	xxx (xx.x%)
MARKED SEVERITY	xxx (xx.x%)
MODERATE SEVERITY	xxx (xx.x%)
MILD SEVERITY	xxx (xx.x%)
VERY MILD SEVERITY	xxx (xx.x%)
NO SEIZURES	xxx (xx.x%)
NOT ASSESSED	xxx (xx.x%)

38

CONFIDENTIAL

RM2009/00475/00  
 VRX-RET-E22-304

Program Path/sas program name

Run Date:

Valeant Pharmaceuticals North America  
 Protocol Number: VRX-RET-E22-304

PAGE X OF X

TABLE 6 NUMBER OF BACKGROUND AEDs AT BASELINE N (%)  
 SAFETY POPULATION

CATEGORY	RETIGABINE (N=XXX)
NUMBER OF AEDs	
1	xxx (xx.x%)
2	xxx (xx.x%)
3	xxx (xx.x%)
VAGAL NERVE STIMULATOR USED?	
YES	xxx (xx.x%)
NO	xxx (xx.x%)

39

CONFIDENTIAL

RM2009/00475/00  
 VRX-RET-E22-304

Program Path/sas program name

Run Date:

Valeant Pharmaceuticals North America  
 Protocol Number: VRX-RET-E22-304

PAGE X OF X

TABLE 7 PRESENCE OF PARTIAL SEIZURE BY SUBTYPE DURING BASELINE PERIOD  
 SAFETY POPULATION

CATEGORY	RETIGABINE (N=XXX)
BASELINE PERIOD	
N	xxx
SIMPLE PARTIAL SEIZURES WITH MOTOR SIGNS	xxx (xx.x%)
SIMPLE PARTIAL SEIZURES WITHOUT MOTOR SIGNS	xxx (xx.x%)
SIMPLE PARTIAL SEIZURES WITH AND WITHOUT MOTOR SIGNS	xxx (xx.x%)
COMPLEX PARTIAL SEIZURES	xxx (xx.x%)
PARTIAL SEIZURES EVOLVING TO SECONDARY GENERALISED	xxx (xx.x%)

40

CONFIDENTIAL

RM2009/00475/00  
 VRX-RET-E22-304

Program Path/sas program name

Run Date:

Valeant Pharmaceuticals North America  
Protocol Number: VRX-RET-E22-304

PAGE X OF X

FOOTNOTES: A PATIENT CAN APPEAR IN MULTIPLE CATEGORIES.

41

CONFIDENTIAL

RM2009/00475/00  
VRX-RET-E22-304

---

Program Path/sas program name

Run Date:

---

Filename: 87272\_304\_SAP\_v2\_final

page 40 of 148

Valeant Pharmaceuticals North America  
 Protocol Number: VRX-RET-E22-304

PAGE X OF X

TABLE 8 PERCENTAGE CHANGE IN MONTHLY TOTAL PARTIAL SEIZURE FREQUENCY  
 SAFETY POPULATION

STATISTICS	RETIGABINE (N=XXX)		
	OBSERVED	CHANGE FROM BASELINE	PERCENTAGE CHANGE FROM BASELINE
BASELINE [1]			
N	xxx		
MEAN	xxx.x		

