STD	xxx.xx		
MEDIAN	xxx.x		
MINIMUM	xxx		
MAXIMUM	xxx		
OPEN-LABEL PHASE			
N	xxx	xxx	xxx
MEAN	xxx.x	xxx.x	xxx.x
STD	xxx.xx	xxx.xx	xxx.xx
MEDIAN	xxx.x	xxx.x	xxx.x
MINIMUM	xxx	xxx	xxx
MAXIMUM	xxx	xxx	xxx

42

CONFIDENTIAL

RM2009/00475/00  
 VRX-RET-E22-304

Valeant Pharmaceuticals North America  
Protocol Number: VRX-RET-E22-304

PAGE X OF X

FOOTNOTE:

[1] BASELINE PHASE IN STUDY VRX-RET-E22-302

43

CONFIDENTIAL

RM2009/00475/00  
VRX-RET-E22-304

---

Program Path/sas program name

Run Date:

---

Filename: 87272\_304\_SAP\_v2\_final

page 42 of 148

Valeant Pharmaceuticals North America  
 Protocol Number: VRX-RET-E22-304

PAGE X OF X

TABLE 9.1 PERCENTAGE CHANGE IN MONTHLY TOTAL PARTIAL SEIZURE FREQUENCY FOR PATIENTS TREATED WITH RETIGABINE FOR AT LEAST 1 MONTH DURING THE OPEN-LABEL EXTENSION SAFETY POPULATION

STATISTICS	RETIGABINE (N=XXX)		
	OBSERVED	CHANGE FROM BASELINE	PERCENTAGE CHANGE FROM BASELINE
BASELINE [1]			
N	xxx		
MEAN	xxx.x		
STD	xxx.xx		
MEDIAN	xxx.x		
MINIMUM	xxx		
MAXIMUM	xxx		
MONTH 1			
N	xxx	xxx	xxx
MEAN	xxx.x	xxx.x	xxx.x
STD	xxx.xx	xxx.xx	xxx.xx
MEDIAN	xxx.x	xxx.x	xxx.x
MINIMUM	xxx	xxx	xxx
MAXIMUM	xxx	xxx	xxx

44

CONFIDENTIAL

RM2009/00475/00  
 VRX-RET-E22-304

Program Path/sas program name

Run Date:

Valeant Pharmaceuticals North America  
Protocol Number: VRX-RET-E22-304

PAGE X OF X

FOOTNOTE: [1] BASELINE PHASE IN STUDY VRX-RET-E22-302

45

CONFIDENTIAL

RM2009/00475/00  
VRX-RET-E22-304

---

Program Path/sas program name

Run Date:

---

Filename: 87272\_304\_SAP\_v2\_final

page 44 of 148

Valeant Pharmaceuticals North America  
 Protocol Number: VRX-RET-E22-304

PAGE X OF X

TABLE 9.2 PERCENTAGE CHANGE IN MONTHLY TOTAL PARTIAL SEIZURE FREQUENCY FOR PATIENTS TREATED WITH RETIGABINE FOR AT LEAST 3 MONTHS DURING THE OPEN-LABEL EXTENSION SAFETY POPULATION

STATISTICS	RETIGABINE (N=XXX)		
	OBSERVED	CHANGE FROM BASELINE	PERCENTAGE CHANGE FROM BASELINE
BASELINE [1]			
N	xxx		
MEAN	xxx.x		
STD	xxx.xx		
MEDIAN	xxx.x		
MINIMUM	xxx		
MAXIMUM	xxx		
MONTH 1			
N	xxx	xxx	xxx
MEAN	xxx.x	xxx.x	xxx.x
STD	xxx.xx	xxx.xx	xxx.xx
MEDIAN	xxx.x	xxx.x	xxx.x
MINIMUM	xxx	xxx	xxx
MAXIMUM	xxx	xxx	xxx
MONTH 3			
N	xxx	xxx	xxx
MEAN	xxx.x	xxx.x	xxx.x
STD	xxx.xx	xxx.xx	xxx.xx
MEDIAN	xxx.x	xxx.x	xxx.x
MINIMUM	xxx	xxx	xxx
MAXIMUM	xxx	xxx	xxx

46

CONFIDENTIAL

RM2009/00475/00  
 VRX-RET-E22-304

Program Path/sas program name

Run Date:

Valeant Pharmaceuticals North America  
Protocol Number: VRX-RET-E22-304

PAGE X OF X

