TABLE 11.10 RESPONDER RATE ( $\geq 50\%$  REDUCTION IN MONTHLY TOTAL PARTIAL SEIZURE FREQUENCY) FOR PATIENTS TREATED WITH RETIGABINE FOR AT LEAST 32 MONTHS DURING THE OPEN-LABEL EXTENSION  
TABLE 11.11 RESPONDER RATE ( $\geq 50\%$  REDUCTION IN MONTHLY TOTAL PARTIAL SEIZURE FREQUENCY) FOR PATIENTS TREATED WITH RETIGABINE FOR AT LEAST 36 MONTHS DURING THE OPEN-LABEL EXTENSION

**PROGRAMMING NOTE: EVERY TIMEPOINT SHOULD BE INCLUDED WITHIN THE INDICATED DURATION OF OPEN-LABEL TREATMENT. E.G. MONTHS 1, 3, 6, 9, 12, 16, 20, 24, 28, 32 AND 36 WILL BE PRESENTED IN TABLE 11.11.**

52

CONFIDENTIAL

RM2009/00475/00  
VRX-RET-E22-304

Program Path/sas program name

Run Date:

Valeant Pharmaceuticals North America  
Protocol Number: VRX-RET-E22-304

PAGE X OF X

TABLE 12 PROPORTION OF PATIENTS EXPERIENCING A REDUCTION IN MONTHLY TOTAL PARTIAL SEIZURE FREQUENCY  
SAFETY POPULATION

CATEGORY	RETIGABINE (N=XXX)
REDUCTION CATEGORY	
[-100%, -75%]	xx (xx.x%)
(- 75%, -50%]	xx (xx.x%)
(- 50%, -25%]	xx (xx.x%)
(- 25%, 0%)	xx (xx.x%)
WITHOUT REDUCTION	xx (xx.x%)

53

CONFIDENTIAL

RM2009/00475/00  
VRX-RET-E22-304

Program Path/sas program name

Run Date:

TABLE 13 PROPORTION OF SEIZURE-FREE DAYS  
SAFETY POPULATION

STATISTICS	RETIGABINE (N=XXX)
SEIZURE-FREE DAYS (%)	
N	xxx
MEAN	xxx.x
STD	xxx.xx
MEDIAN	xxx.x
MINIMUM	xxx
MAXIMUM	xxx
REDUCTION CATEGORY	
SEIZURE-FREE [=100%]	xx (xx.x%)
NOT SEIZURE-FREE	xx (xx.x%)
[95%, 100%]	xx (xx.x%)
[75%, 95%]	xx (xx.x%)
[50%, 75%]	xx (xx.x%)
[50%, 25%]	xx (xx.x%)
[0%, 25%]	xx (xx.x%)
NUMBER OF PATIENTS WHO WERE SEIZURE-FREE FOR	
6 MONTHS	xx (xx.x%)
12 MONTHS	xx (xx.x%)

54

CONFIDENTIAL

RM2009/00475/00  
VRX-RET-E22-304

TABLE 14 EXTENT OF EXPOSURE TO STUDY MEDICATION  
 SAFETY POPULATION

STATISTICS	RETIGABINE (N=XXX)
EXTENT OF EXPOSURE (DAYS)	
N	xxx
MEAN	xxx.x
STD	xxx.xx
MEDIAN	xxx.x
MINIMUM	xxx
MAXIMUM	xxx
RETIGABINE EXPOSURE CATEGORY (MONTHS)	
N	xxx (100.0%)
[0, 1]	xxx ( xx.x%)
(1, 3]	xxx ( xx.x%)
(3, 6]	xxx ( xx.x%)
(6, 9]	xxx ( xx.x%)
(9, 12]	xxx ( xx.x%)
(12,16]	xxx ( xx.x%)
(16,20]	xxx ( xx.x%)
(20,24]	xxx ( xx.x%)
(24,28]	xxx ( xx.x%)
(28,32]	xxx ( xx.x%)
(32,36]	xxx ( xx.x%)
>36	
DAILY DOSE OF RETIGABINE EXPOSURE (MG)	
N	xxx
MEAN	xxx.x
STD	xxx.xx
MEDIAN	xxx.x
MINIMUM	xxx
MAXIMUM	xxx

55

CONFIDENTIAL

RM2009/00475/00  
 VRX-RET-E22-304

TABLE 15 NUMBER (%) OF PATIENTS REPORTING TREATMENT-EMERGENT ADVERSE EVENTS  
 SAFETY POPULATION

SYSTEM ORGAN CLASS PREFERRED TERM	RETIGABINE (N=XXX)
ANY ADVERSE EVENT	xxx ( xx.x%)

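### SAP 4.4 sets the open-label partial-seizure rate against an all-seizure baseline in two sentences, contradicting the rest of the section and the titles of Tables 8, 10 and 12

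*SAP*

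**What the plan says.** The first paragraph of SAP 4.4 (Efficacy Evaluation) defines two monthly rates. The total partial rate counts partial seizures. The total "rate is defined as the sum of partial and generalized (or unclassified) seizures throughout the open-label duration in days".

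The second paragraph introduces the overall percent change, its classes and the responder rate (a reduction of at least 50%). It opens: "Monthly total partial seizure rates observed during the open-label extension period will be compared to the monthly total seizure rates" of the baseline phase of the double-blind study. It continues: "The baseline monthly total seizure rates will only be derived for patients who enter this open-label extension" and have an open-label partial rate. The third sentence changes the basis: "The percent change in monthly total partial seizure rates from the Baseline phase will be classified into" the five bands.

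The third paragraph, which governs Tables 9.x and 11.x, is explicit: "The monthly total partial seizure rates compared to the baseline monthly total partial seizure rate will be presented cumulatively for each timepoint".

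The table shells in SAP section 10 follow the partial reading in their titles: "TABLE 8 PERCENTAGE CHANGE IN MONTHLY TOTAL PARTIAL SEIZURE FREQUENCY" and "TABLE 12 PROPORTION OF PATIENTS EXPERIENCING A REDUCTION IN MONTHLY TOTAL PARTIAL SEIZURE FREQUENCY"; the Table 10 title also says partial. The Table 8 footnote identifies the baseline period but not the seizure type.

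The protocol is itself split. The synopsis bases the difference and percent change on the baseline partial rate. Protocol 11.1 compares and classifies total against total.

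**The concern.** Two adjacent sentences put partial seizures in the numerator and all seizures in the denominator. They introduce the overall percent change, which SAP 3.2.1 names as the primary efficacy variable, and the responder rate reported with it.

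If they are programmed literally, a patient with generalized or unclassified seizures at baseline is credited with a reduction because those seizures are left out of the open-label count. The overall tables (8, 10, 12) would then use a different baseline from the cohort tables (9.x, 11.x) while both carry the word partial in their titles.

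The sentences cannot be read as belonging to a separate total-seizure analysis, because no table in SAP sections 7 or 10 reports a total-seizure rate. For the same reason the total-against-total comparison in protocol 11.1 has no output. SAP 4.8 nevertheless records no change to the planned analysis.

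**Working it through.** The documents give no expected responder rate or sample-size calculation for this study, so there is no planned figure to reproduce.

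**1. The texts side by side**

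| Place | Open-label rate | Baseline rate |
|---|---|---|
| SAP 4.4, para 2, sentence 1 | partial | **total** |
| SAP 4.4, para 2, sentence 2 | partial | **total** |
| SAP 4.4, para 2, sentence 3 | partial | partial (implied) |
| SAP 4.4, para 3 | partial | partial |
| Titles of Tables 8, 10, 12 | partial | partial (implied) |
| Protocol synopsis | partial (implied) | partial |
| Protocol 11.1 | total | total |

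Only the first two rows mix seizure types.

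**2. Direction and size for one patient**

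Let P be the baseline partial rate, G the baseline generalized or unclassified rate, p the open-label partial rate, and g = G/(P+G). The true partial reduction is r = 1 − p/P. The literal reduction is

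1 − p/(P+G) = 1 − (1−r)(1−g).

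Since g ≥ 0, this is never below r. It equals r when G = 0 or p = 0. Example with P = 8 and G = 2 per 28 days:

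- p = 5: (8−5)/8 = 37.5% true; (10−5)/10 = 50.0% literal. A non-responder becomes a responder.
- p = 9: a 12.5% increase true; (10−9)/10 = 10% reduction literal. The patient leaves the worsened class.

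Setting the literal reduction to 50% gives the true reduction needed to count as a responder, 1 − 0.5/(1−g). The documents do not give g, so three values are assumed:

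| g (assumed) | True reduction needed | A true 45% reduction reads as |
|---|---|---|
| 5% | 1 − 0.5/0.95 = 47.4% | 1 − 0.55×0.95 = 47.8% |
| 10% | 1 − 0.5/0.90 = 44.4% | 1 − 0.55×0.90 = 50.5% |
| 20% | 1 − 0.5/0.80 = 37.5% | 1 − 0.55×0.80 = 56.0% |

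Partial seizures that evolve to secondarily generalized ones are listed as partial (Table 7, Listing 7). Only the types in Listing 8 add to g.

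**3. Study-level illustration**

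The anchor is the predecessor extension in protocol 7.4: 103/222 = 46.4% responders and a median decrease of 48.3%, that is, a median ratio of open-label to baseline rate of 0.517. Assume lognormal ratios. The log SD that fits both figures is ln(0.5/0.517)/z(0.464) = 0.37. The responder proportion among affected patients is Φ[(ln(0.5/(1−g)) − ln 0.517)/0.37] = 51.9%, 57.7% and 69.6% for g = 5%, 10% and 20%. If a share s of patients is affected, the reported rate is (1−s)×46.4% plus s times that proportion:

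| s (assumed) | g = 5% | g = 10% | g = 20% |
|---|---|---|---|
| 5% | 46.7% | 47.0% | 47.6% |
| 10% | 47.0% | 47.5% | 48.7% |
| 20% | 47.5% | 48.7% | 51.0% |

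The gain is +0.3 to +4.6 points. With a wider spread (log SD 1.0, median ratio reset to 0.547 to keep 46.4% responders), the range is 46.5% to 48.2%, a gain of +0.1 to +1.8 points.

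**The case against.** The best reply is that the documents largely settle the matter. The sentence that says what is classified is partial against partial, as are the next paragraph, the table titles and the synopsis. The two faulty sentences give no formula. A programmer would have to override all of that to produce the inflated result. This stands as a reason to expect a slip rather than a deliberate choice. It does not remove two sentences that name the wrong baseline rate, and the titles do not state a baseline type separately.

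The Table 8 footnote is weak evidence alone: the same footnote appears under Tables 9.1 and 9.2, which are not in question. That is fair; it fails to resolve the ambiguity but does not create it.

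SAP 4.4 defines both rates for the open-label period only, so applying the definitions to baseline is an inference. It is the natural one, and no other definition is offered.

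The study-level range is fragile, and this stands too. The log SD of 0.37 rests on two nearly coincident points. Holding the median, a responder rate of 45% would give 0.27 and 48% would give 0.67, both within one standard error (√(0.464×0.536/222) ≈ 3.3 points). It also implies that only about 3.7% of patients worsen. The log SD of 1.0 no longer matches the 48.3% median decrease. The Table 4 footnote shows that a generalized history may be recorded, not that such seizures occurred in the 8-week baseline.

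Finally, protocol 11.1 compares like with like and causes no inflation. It matters here only because it leaves the protocol without one clear comparator and has no matching output.

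**Conclusion.** The concern holds. SAP 4.4 contradicts itself on the baseline seizure type for the overall percent change and responder rate, and the literal version can only favour the drug. Confidence is high for the contradiction and its direction.

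The size cannot be fixed from the documents. It is zero if partial against partial is programmed. Otherwise it is confined to patients with generalized or unclassified baseline seizures and at least one open-label partial seizure. The per-patient results are exact given g. The study-level gain of +0.1 to +4.6 points depends on assumed values for g, the share affected and the lognormal spread, and should be read as an illustration.

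Tables 9.x and 11.x and Figure 1 fall under the paragraph that already specifies a partial baseline and are not claimed to be affected. Efficacy is a secondary, descriptive objective in a single-arm extension. This should be fixed, but it does not threaten the primary safety objective.

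**What to change.** - In the first two sentences of the second paragraph of SAP 4.4, change the baseline rate to the monthly total *partial* seizure rate.
- State the seizure type in the Table 8 baseline footnote.
- If a total-seizure analysis is wanted, report it as total against total in its own table.
- Reconcile protocol 11.1 with the synopsis so that both name the same comparison.

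The cost is two SAP sentences, one footnote and one protocol paragraph, with no new data. One extra table shell is needed if the total-seizure analysis is kept. Some patients will show a slightly smaller reduction than under the literal reading.
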